***Standard corticosteroids tapering regimen (ECS)**

Week	1	2	3	4	5	6	7	8	9	10
CS mg/day	40	40	35	30	25	20	15	10	5	5 mg every other day

***Short course corticosteroids tapering regimen (ECSC)**

Day	1	4	7	10	13	16				
CS mg/day	40	30	20	10	5	5 every other day	0	0	0	0

INSTRUCTIONS FOR FOOD REINTRODUCTION AFTER 6 WEEKS OF EXCLUSIVE ENTERAL NUTRITION

<https://www.qegateshead.nhs.uk/sites/default/files/users/user1/leaflets/IL382%20Modul en%20IBD%20-%20Reintroduction%20of%20foods.pdf>

After 6 weeks on exclusive formula feeding, it is time to reintroduce all of the food you have removed during the program. The purpose of doing this very slowly is to give time to the gut to adapt to the diet. Transition to normal foods must be done with care, foods should be gradually reintroduced over a period of two to four weeks, however, it may be necessary to reintroduce foods more slowly.

In order to accomplish this, please introduce each of the following food groups for the period of time suggested in each stage, ideally respecting the order. If you do have a reaction, such as headache, rash, brain fog, fatigue, digestive reaction or other symptom you are familiar with, write it down in the food reintroduction chart below or a food journal so you don't forget later. If you discover a particular food isn't good for you, remove it again. The food reaction should go away within a day or 2. If you are not used to take any of the foods from the list, it is ok to skip it. When you have finished reintroducing all the foods from the list, a free diet is allowed.

Start date:

Stage 1: (Two days) with $\frac{1}{2}$ of IBD formula

Initially fluids not containing dairy, eg tea or coffee black or with soya milk, fruit juice, fruit squash, Oxo, carbonated drinks, sieved soup, jelly or ice lollies.

Stage 2: (Five days) with $\frac{1}{2}$ of IBD formula

Introduction of a few soft foods eg fish, chicken, egg, rice and potato. Small frequent snacks should be encouraged instead of one or two larger meals.

Stage 3: (Five days) with $\frac{1}{4}$ of IBD formula

Gradually increase the variety of foods in the diet continuing to keep the fibre and fat content low, eg red meat, stewed or peeled fruit, very well-cooked vegetables. The portion size of meals should be gradually increased with the number of snacks reduced.

Stage 4: (Three days) with $\frac{1}{4}$ IBD formula

Addition of bread and other gluten containing foods ie pasta, cereal, bread, biscuits, crackers, cakes, sausages.

Stage 5: (Three days) No IBD formula

Inclusion of milk or milk derivatives (if you are not lactose intolerant) ie margarine, butter, milk, cream, ice cream, yoghurts, fromage frais, milk pudding, custard.

Stage 6: Gradually increase dietary fibre, fried and spicy food if desired. It may be an idea to keep a food and symptom diary recording the food you eat. See below for an example.

Protocol date: October 2018

If you have any reaction to any food or food group, avoid adding anymore new foods. After three days you may return to the food reintroduction avoiding any suspect foods

FOOD REACTION LOG

Table : Food reintroduction (Sanderson et al, Arch Dis Child 1987; 61:123-127)

Table 3 Food reintroduction programme six weeks after starting Flexical

Each new food is reintroduced into the diet four days after the previous food in the following order:

Potatoes
Lamb
Pears
Chicken
Yeast (Brewer's Yeast Tablets)
Wheat (spaghetti)
Bread (wholemeal)
Cabbage
Rice
Apple
Carrot
Beef
Milk
Butter
Cheese
Eggs

A free diet is allowed once these foods have been started

Rationale for rapid introduction of foods vs standard (Faiman A, et al. Standard versus rapid food reintroduction after exclusive enteral nutritional therapy in paediatric Crohn's disease. Eur J Gastroenterol Hepatol. 2014 Mar;26(3):276-81)

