- Systemic priming to gut bacteria ([name] Lab using Flow cytometry after incubating patients' serum with cultured fecal bacteria¹⁶)
- First urine morning for metabolomics
- Intestinal permeability – indirect markers of mucosal integrity (FABP2)

Statistical analysis

There is no previous estimate on the effect of ECS compared to CS in inducing symptomatic improvement and associated changes in gut microbiota composition. Therefore, a sample size of 30 patients per arm^{28,29} should be sufficient to estimate the results and allow us to plan for future larger study. We will recruit additional 10 patients in total, to account for drop outs rates. Results will be analyzed as intention to treat (for primary outcome) and per protocol (excluding patients non-compliant with EN). The results will be expressed as n (%), mean (SD) or median (IQR) as appropriate. We will perform logistic regression to assess the association between symptomatic response and significant changes in gut microbiota composition in each group. T test or Man Whitney U test will be used as appropriate to assess differences between means. Analysis will be performed using SPSS version 21 (San Diego, CA).

Early withdrawals:

The following criteria will be considered as reasons for early discontinuation from the study (drop outs):

- Patient's decision.

- Physician's decision in case that the continuation of the patient in the study places him/her at risk.
- Patients that were not compliant with the unauthorized concomitant diets/treatments/medication will be considered as non-compliant and considered for the ITT analysis. If a subject's outcome measures worsen to the degree that they meet the study's Exclusion Criteria, study treatment will be withdrawn. Medical care will be provided as directed by the study physician and/or the subject's physician. If the required medical care conflicts with the study protocol, the subject will be placed in the intent-to-treat group. Study safety follow up will continue unless the subject withdraws, and/or is withdrawn by the study physician, and/or on the advice of the subject's physician.

Handling of adverse events

Reporting and documentation of adverse events

All adverse events occurring during the study will be reported and recorded whether or not they are considered to be non-serious, serious and/or related to the treatment. The following information will be required in each case:

- Subject and date
- Description of event
- Duration
- Frequency

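### The food-reintroduction leaflet lets a patient resume adding foods three days after a reaction, whether or not the symptom has cleared (minor safety wording)

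*Combined protocol and SAP*

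**What the plan says.** The leaflet is headed *Instructions for food reintroduction after 6 weeks of exclusive enteral nutrition* and applies to the ECS and ECSC arms. It asks patients to write down reactions and to take out a food that does not suit them. It gives an expected course: "The food reaction should go away within a day or 2". It also allows for a slower pace: "it may be necessary to reintroduce foods more slowly". At the end comes the instruction for a patient who reacts: "If you have any reaction to any food or food group, avoid adding anymore new foods", followed by "After three days you may return to the food reintroduction avoiding any suspect foods". *Follow up after treatment* places reintroduction and the matching formula reduction under a nutrition expert and gives no contact schedule.

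For worsening in general, *Early withdrawals* acts when a subject's "outcome measures worsen to the degree that they meet" the study's "Exclusion Criteria, study treatment will be withdrawn". It adds that "Medical care will be provided as directed by the study physician" or the patient's own physician, and that "Study safety follow up will continue unless the subject withdraws" or is withdrawn on medical grounds.

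**The concern.** The restart permission has no condition attached. The leaflet's own examples of a reaction include fatigue and digestive upset, which overlap with active Crohn's disease. A patient whose symptom is really the start of a flare could take it for a food reaction, drop one item, wait three days and carry on while the formula is being cut. The leaflet text does not say what to do if a symptom lasts longer than expected, and no scheduled visit would pick it up before week 10.

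The worsening rule raises a smaller, related point. It is framed in terms of outcome measures but refers to a list that contains none, so staff have no usable wording for when worsening disease activity should prompt a medical review.

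**Working it through.** **Who receives the leaflet.** The plan's total reproduces: 3 × 30 = 90, and 90 / (1 − 0.10) = 100 (*Participants*). The two EEN arms hold 2 × 30 = 60 patients after dropout, or 2/3 × 100 ≈ 67 as recruited.

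**The gap between visits.** Visit 3 is at week 6 and visit 4 at week 10 (*Study design*). Counting both from visit 2, the gap is 70 − 42 = 28 days. It is shorter if enrolment means the screening visit.

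**What falls in the gap.**
- Leaflet stages 1–2: 2 + 5 = 7 days at half formula (reintroduction days 1–7).
- Stages 3–4: 5 + 3 = 8 days at quarter formula (days 8–15).
- Stage 5: 3 days with no formula (days 16–18).
- Total: 7 + 8 + 3 = 18 timed days, with formula cuts on days 8 and 16 if there is no pause. All 18 fall inside a 28-day gap.
- At the alternative pace in *Follow up after treatment*, one item every 2 days, the 16 listed foods start on days 1, 3, …, 31. By day 28, 1 + floor(27/2) = 14 of the 16 have started.

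So most or all of reintroduction takes place without a scheduled visit under either schedule. Steroid cover is also low: the standard taper gives 15, 10 and 5 mg/day and then 5 mg on alternate days in weeks 7–10, and the ECSC short course has already ended.

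**What the three-day rule does.** Suppose a reaction occurs on day d. The leaflet expects it to clear by d + 2 and permits restart from d + 3.
- If it clears by d + 2, requiring clearance before restart changes nothing.
- If it is still present on d + 3, it has outlasted the leaflet's expectation, and the current wording still permits restart.

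The missing condition therefore matters only for symptoms that are not behaving like the food reaction the leaflet describes. As an illustration, take a reaction on day 5. Restart is permitted from day 5 + 3 = 8, which is also the day formula goes from a half to a quarter. The leaflet does not say whether a pause in foods also holds the formula timetable.

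**The worsening rule.** Set against the eligibility lists:
- Exclusion criteria naming CDAI, HBI, CRP or calprotectin: 0 of 10.
- Inclusion criteria naming one of them: 2 of 4 (criteria 3 and 4).
- Exclusion criteria 1 (current EEN) and 5 (recent prednisone) are met through the assigned treatment itself.

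Read literally, the exclusion list cannot serve as a threshold for worsening.

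**The case against.** The leaflet wording is permissive rather than directive, rules out suspect foods, waits a day beyond the expected recovery time and allows a slower pace. A nutrition expert oversees reintroduction and the formula reduction, and all adverse events are to be recorded. A telephone instruction may sit in the contact or consent pages, which are not available here. All of this stands and keeps the point small. None of it makes restart depend on recovery, and the supervision has no stated contact schedule.

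On the worsening rule the objection is stronger. The rule governs withdrawal of study treatment, not detection of relapse, and can sensibly be read as aimed at complications such as obstruction, abscess or stricture. Several routes already allow action on a flare: the investigator clause in exclusion criterion 2, criterion 10, the physician's-decision reason for withdrawal, physician-directed care and continued safety follow-up. Changing a biologic or immunosuppressant to treat a relapse would also meet exclusion criterion 6, although only after someone had recognised the relapse. This reduces the second point to a clarification.

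A reader might infer that a relapsing patient is left with no route to care or withdrawal. The routes just listed contradict that. A reader might also conclude that the plan needs a fixed CDAI trigger, such as a rise of 70. The secondary outcomes use a drop of more than 70 to define improvement, but nothing in the documents supports the reverse as a threshold for worsening. Nor could such a trigger fire unless a score were taken.

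**Conclusion.** The leaflet point holds as a cheap, minor safety improvement: the restart rule is a clock where it should be conditional on recovery. It applies to the two EEN arms after week 6 and does not affect the week-6 remission endpoint. The counts above (60 to 67 patients, up to 28 days, 18 timed days) show where the rule operates. They do not measure harm, and no number of missed flares can be derived from the documents.

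The worsening rule deserves rewording in all three arms because its cross-reference supplies no measure of disease activity. It does not show that relapse goes unmanaged.

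The conclusion assumes that the leaflet is handed out as printed, and that the unseen pages and the nutrition expert do not already make restart conditional on recovery. A call-us line alone would cover part of the fix but would leave the restart sentence as it is.

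**What to change.** **Leaflet (main change).** State that new foods, and the next reduction in formula, resume only once the symptom has gone, keeping the three-day pause as a minimum. Tell the patient to call the study team if the symptom lasts more than 2 days or suggests a flare.

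**Early withdrawals (clarification).** Replace the general reference to the exclusion criteria. Study treatment is withdrawn for the complications in exclusion criteria 2–3 or on the physician's decision. Separately, clinically judged worsening of disease activity prompts a medical review, in the same way in all three arms. Whether to attach a CDAI or HBI cut-off is for the investigators to decide. An absolute CDAI >220 or HBI >6 should not be a withdrawal trigger before week 6, because patients who enter on symptoms meet it at baseline.

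**Cost.** Two lines in the leaflet and one or two sentences in the protocol. Some extra calls will follow, and some mild food reactions will be reviewed that would have settled by themselves. No added visit is required.

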Appendix 2-Steroids adverse events assessment (visit 2)

	Yes/no	Comments
1. Moon face		
2. Bloating		
3. Swelling		
4. Weight gain		
5. Increase appetite		
6. Hair loss		
7. Acne		
8. Stretch marks		
9. Insomnia, restlessness and or trouble sleeping		
10. Anxiety or nervousness		
11. Depression		
12. Anger/irritability		
13. Generalized weakness or fatigue		
14. Joint pain		
15. Hot flushes		
16. Visual problems (light sensitivity, decreased visual acuity)		
17. Nausea, vomiting		
18. Diarrhea		
19. Dizziness		
20. Headaches		
21. Hypertension		
22. High glucose levels		

Nestlé Nutrition Flavour Mix

Description

Nestlé Nutrition Flavour Mix is a flavouring powder formulated for use with Peptamen® Vanilla Cup and Modulen® IBD.

Presentation

60g tub (with a 0.6g scoop). Available in 5 flavours: Banana, Lemon & Lime, Chocolate, Strawberry and Coffee.

Indications

ACBS approved, prescribable on FP10 (GP10 in Scotland). For use with Vanilla flavoured Peptamen® and Modulen® IBD.

Ingredients

Banana Flavour

Dextrose, Flavouring (contains Maltodextrin), Maltodextrin, Anti-caking agent (Silicon dioxide), Colour (Curcumin), Sweetener (Sucralose).

Coffee Flavour

Dextrose, Soluble Coffee solids, Anti-caking agent (Silicon dioxide), Colour (Caramel E150c), Sweetener (Sucralose).

Strawberry Flavour

Dextrose, Flavouring (contains Maltodextrin), Acidity regulators (Lactic acid, Acetic acid), Stabiliser (Gum arabic), Preservative (Sulphur dioxide), Anti-caking agent (Silicon dioxide), Colour (Beetroot red), Sweetener (Sucralose).

Lemon & Lime Flavour

Dextrose, Flavouring (contains Maltodextrin), Modified starch, Antioxidant (E320), Citric acid, Anti-caking agent (Silicon dioxide), Colour (Curcumin), Sweetener (Sucralose).

Chocolate Flavour

Dextrose, Flavouring (contains Maltodextrin), Stabilisers (Glycerine, Gum arabic), Molasses, Anti-caking agent (Silicon dioxide), Colour (Caramel E150c), Sweetener (Sucralose).

All Flavours: Milk, Egg, Soya, Nut, Gluten and Lactose free.

Administration and dosage

Suggested intake: Add 2 scoops Nestlé Nutrition Flavour Mix per 100ml.

Shelf life and storage

Shelf life of 12 months from date of manufacture when stored at room temperature.

Contraindications

Not for intravenous use.

Not suitable for children under 3 year of age.

Precautions

To be used with caution in children between 3 and 5 years of age.

Suitable for use in children over 5 years of age.

Must be used under medical supervision.

Nutrition information (All flavours)

Nutrients	Nutrient content per scoop (0.6g)	Nutrient content per 100g
General		
Energy (kcal/kJ)	2.04/8.2	340/1360
Protein (g)	Nil	Nil
Fat (g)	Nil	Nil
Carbohydrate (g)	0.51	85

Osmolality information

The addition of Nestlé Nutrition Flavour Mix to Modulen® IBD or Peptamen® will increase the osmolality.

As a guide the following increases will occur (based on the addition of 2 scoops of Nestlé Nutrition Flavour Mix to 100ml Modulen® IBD standard concentration):

Change in Osmolality (mOsm/kg)

Nestlé Nutrition Flavour Mix Strawberry	+60
Nestlé Nutrition Flavour Mix Coffee	+72

BMR calculation for men (metric)

BMR = $66.47 + (13.75 \times \text{weight in kg}) + (5.003 \times \text{height in cm}) - (6.755 \times \text{age in years})$

BMR calculation for women (metric)

BMR = $655.1 + (9.563 \times \text{weight in kg}) + (1.850 \times \text{height in cm}) - (4.676 \times \text{age in years})$

Activity factor:

Sedentary. Little to no regular exercise.

(factor 1.2)

Mild activity level: Intensive exercise for at least 20 minutes 1 to 3 times per week. This may include such things as bicycling, jogging, basketball, swimming, skating, etc. If you do not exercise regularly, but you maintain a busy life style that requires you to walk frequently for long periods, you meet the requirements of this level.

(factor 1.375)

Moderate activity level: Intensive exercise for at least 30 to 60 minutes 3 to 4 times per week. Any of the activities listed above will qualify. (factor 1.55)

Heavy or (Labor-intensive) activity level: Intensive exercise for 60 minutes or greater 5 to 7 days per week (see sample activities above). Labor-intensive occupations also qualify for this level. Labor-intensive occupations include construction work (brick laying, carpentry, general labor, etc.). Also farming, landscape worker or similar occupations. (factor 1.7)

Extreme level: Exceedingly active and/or very demanding activities: Examples include: (1) athlete with an almost unstoppable training schedule with multiple training sessions throughout the day (2) very demanding job, such as shoveling coal or working long hours on an assembly line. Generally, this level of activity is very difficult to achieve. (factor 1.9)

Calculator: <http://www.globalrph.com/harris-benedict-equation.cgi>

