Potential mechanisms by which EEN might act include relative bowel rest, reduced antigenic load, provision of trophic amino acids, local anti-inflammatory effects, and modification of gut microbiota^{11,20}. However, there is no strong evidence to fully support any one of these mechanisms. A recent meta-analysis²⁰ showed that the effects of the therapeutic formula on specific bacterial strains were variable and inconsistent among studies, possibly due to small sample sizes and methodological limitations. Our preliminary data showed that short term dietary changes improve motility in patients with low-grade gut inflammation²¹. However, the effects of EEN on gastrointestinal transit in adults has not been yet investigated.

Evidence for the effect of EEN on quality of life, an essential patient reported outcome, is particularly scarce. Guo *et al*³⁰ found an improvement of quality of life in 13 patients with CD receiving EEN for 6 weeks. However, it is currently unknown whether EEN is more effective than CS in improving quality of life in adults with CD.

The potentially synergistic effects of adding EEN to CS therapy have not been explored before. Therefore, we designed a randomized controlled trial with the objective to investigate the effect of EEN in addition to different regimes of CS therapy (ECS) compared to CS alone (CS), for decreasing disease activity and improving quality of life in adult patients with CD. We also propose to investigate potential mechanisms underlying any beneficial effect of EEN in CD in the context of concomitant CS therapy.

Hypotheses:

- 1- Six weeks of ECS will be more effective than CS in inducing clinical remission in patients with active CD
- 2- Six weeks of EEN in addition to a short course of CS (ECSC) will have similar efficacy than ECS and reduced number of adverse events
- 3- Six weeks of ECS will lead to beneficial changes in the composition and/or metabolic activity of the intestinal microbiota, gastrointestinal transit and inflammatory burden.

Because the effect size of ECS has not been investigated before, we will perform a pilot study to assess feasibility and calculate estimates of effect size in order to plan a larger trial. Based on the significant number of patients, if the study is feasible, we will consider the sample size estimated through this pilot study for the full trial to minimize the possibility of recruiting additional patients.

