General aim and endpoint: To assess study feasibility and provide estimated effect sizes (point estimates with confidence intervals) for all measures of interest in order to plan an adequately powered study. We will assess recruitment rates and acceptability of treatment in arms involving exclusive enteral nutrition.

Primary outcome and endpoint: To assess the efficacy of 6 weeks of ECS in inducing remission (CDAI <150) compared to treatment with CS in adult patients with active CD (CDAI >220 and either CRP >5 or fecal calprotectin >250 mg/l).

Secondary outcomes and endpoints: To determine the beneficial effect of 6 weeks of ECS as compared to CS in inducing:

1. Clinical disease improvement (drop in CDAI >70 or 100)
2. Improvement in quality of life (using the Inflammatory Bowel Disease Questionnaire (increase IBDQ scores))
3. Biochemical remission (normalization of either serum CRP and/or fecal calprotectin)
4. Changes in microbiota composition (16S sequencing Illumina)
5. Normalization of colonic transit (SHAPE 0-5 markers at day 5)³⁴ among those with altered transit at baseline
6. Decrease in anxiety and/or depression scores (decrease >2 points HAD-A and/or HAD-D scores)
7. Increase in body weight and improvement in nutritional status (increased levels of micronutrients)
8. Decrease of indirect markers of mucosal integrity (IFABP2)
9. Changes in bacterial fermentation profile (SCFAs: acetate (acetic acid), propionate (propionic acid), and butyrate (butyric acid))^{26,27}.
10. Decreased number of adverse events

METHODS

Study design

Protocol date: October 2018

Randomized control trial; 3 arms of treatment: EEN plus standard or short course of CS (ECS, ECSC) vs CS alone (CS) conducted at McMaster University Medical Centre (Figure 1). The study will last 10 weeks and will involve 4 visits. At the screening visit, we will assess clinical history and symptoms, perform a physical exam and complete bloodwork after the informed consent is signed. Randomization will occur at the second visit (pre-treatment), when the inclusion and exclusion criteria and symptoms will be re-assessed, and baseline stool and urine samples will be collected. In addition, we will perform a SHAPE study and patients will be assessed by a dietitian or clinical nutrition support specialist to assess dietary factors and estimate energy needs using the Harris Benedict equation as detailed below.

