Patients randomized to ECS or ECSC arms will receive EEN defined as enteral feeds given exclusively as sole nutritional source over 6 weeks period in addition to the CS therapy. Hypercaloric polymeric formula (Modulen 1.5 kcal /ml; Nestle ^{22,23}) will be used for a period of 6 weeks. To increase palatability, patients will be allowed to add the “Nestle Nutrition Flavour Mix” (see Appendix). Daily volumes of formula will be prescribed based upon the patient’s estimated energy requirement (EER), calculated using the Harris Benedict equation (calculator available at <https://manytools.org/handy/bmr-calculator>), which estimates basal metabolic rate from weight and height and then applies an activity factor which ranges from 1.2 to 2.4 (Sedentary AF 1.2; mild activity 1.375, moderate activity AF 1.55, heavy activity AF 1.7, extreme AF 1.9 For details, refer to Appendix). Actual body weight or ideal body weight for height will be used in the equation depending on whether the patient is of an appropriate weight or underweight for height. Oral administration will be encouraged wherever possible, with formula volume distributed as set meals and snacks throughout the day. Nasogastric (NG) tube insertion for delivery of formula will be discussed and offered only if oral supplementation is not possible or not tolerated by the patient. Enteral feeding will be prescribed as an exclusive therapy, with exclusion of all normal diet for the period of feeding. Patients will be reviewed after 3 weeks of therapy and, when required, energy intakes will be modified by adjusting formula volumes based upon adequacy of weight changes. Volume taken per meal and distribution during the day will be recorded in the case report form. No oral foods or fluids

(except for clear liquids including water and weak tea or coffee) will be allowed during the study period. Vitamins and supplements will be allowed if doses have been stable before entering in the study, and doses are not changed during the study.

2. Corticosteroids

Patients in ECS and CS arms will receive oral prednisone 40 mg x day for 2 weeks; with subsequent taper of daily dose by 5 mg per week. Patients randomized to ECSC arm will receive oral prednisone 40 mg x day for 3 days and taper in 16 days (Figure 1). Patients randomized to the CS arm will be asked to maintain their regular diet.

Follow up after treatment

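### The adverse event comparison of ECS with CS (secondary endpoint 10) has no structured, arm-neutral, on-treatment harm list: the only checklist is steroid-oriented and labelled for a pre-treatment visit.

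*Combined protocol and SAP*

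**What the plan says.** The secondary outcomes are introduced as a two-arm contrast, "To determine the beneficial effect of 6 weeks of ECS as compared to CS in inducing", and item 10 is "Decreased number of adverse events". No instrument, time window or counting rule follows. Hypothesis 2 makes a separate claim for the short-course arm (ECSC): "Six weeks of EEN in addition to a short course of CS (ECSC) will have similar efficacy than ECS and reduced number of adverse events".

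Under Intervention, the steroid course is common to the two arms of endpoint 10: "Patients in ECS and CS arms will receive oral prednisone 40 mg x day for 2 weeks", followed by one taper. The EEN text foresees difficulties with the formula. Flavouring is allowed for palatability, and a nasogastric tube is "offered only if oral supplementation is not possible or not tolerated by the patient".

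The one structured harm form is headed "Appendix 2-Steroids adverse events assessment (visit 2" and has 22 yes/no items. The general rule, under Handling of adverse events, is "All adverse events occurring during the study will be reported and recorded". That section lists what is documented for each event. It does not say whether patients are asked about particular problems or must volunteer them.

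**The concern.** With the same prednisone in both arms, steroid harms should be about equal in ECS and CS. What endpoint 10 can chiefly reveal is what EEN adds or relieves, and the form was not built for that. Its visit label also places it before any study treatment has been given.

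Two things are at stake. One is the safety comparison itself. The other is the stated pilot aim of providing effect estimates for all measures of interest, with acceptability of the EEN arms, to plan a larger trial. An adverse event difference that depends on which questions were asked would carry into that plan.

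**Working it through.** **1. Visit label.** Study design places randomization at visit 2 and calls that visit pre-treatment. Visit 3 comes six weeks later, and visit 4 is ten weeks after enrollment. Exclusion criterion 5 removes patients who took prednisone in the previous 30 days. A steroid checklist at visit 2 therefore records baseline complaints. No section says that it is repeated at visit 3 or 4.

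**2. Items against the contrast.** Given equal prednisone, the 22 items can separate ECS from CS only through EEN effects or change in the disease.
- Items that could register an EEN effect: bloating (2), weight gain (4), increased appetite (5), nausea or vomiting (17), diarrhea (18).
- Not on the form: formula intolerance or refusal, constipation, tube problems.
- Weight gain is a harm on the form but a hoped-for benefit in secondary endpoint 7.

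**3. The plan's own figures.** The documents give no adverse event rate, so there is nothing to reproduce for endpoint 10. The sample size does reproduce: 3 × 30 = 90, and 90 / (1 − 0.10) = 100.

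**4. Illustration if the form is used on treatment (all rates assumed).** Let 30% of EEN patients have an EEN-specific harm and no CS patients have it. Difference shown = true rate × capture.
- Prompted, capture 90%: 0.30 × 0.90 = 27 points.
- Unprompted, capture 30%, 40% or 60%: 0.30 × 0.30 = 9, 0.30 × 0.40 = 12, 0.30 × 0.60 = 18 points.

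**5. When some EEN harms are already listed.** Let g be the share of the true ECS excess that falls on listed items, and s the capture of unlisted events relative to listed ones (both assumed). Share of the excess seen = g + (1 − g)s.

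| g | s = 0.3 | s = 0.5 | s = 0.7 |
|---|---|---|---|
| 0 | 0.30 | 0.50 | 0.70 |
| 0.50 | 0.65 | 0.75 | 0.85 |
| 0.75 | 0.82 | 0.88 | 0.93 |

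The share is always positive. This mechanism reduces an ECS excess but cannot turn it into an ECS advantage.

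**6. Precision at 30 per arm.** Take an unlisted harm truly present in 40% of ECS and 10% of CS patients (assumed). The 95% interval is d ± 1.96 × √[p₁(1 − p₁)/30 + p₂(1 − p₂)/30].
- Full capture: 40% v 10%, d = 30 points, interval 9 to 51, power 0.78.
- Half capture: 20% v 5%, d = 15 points, interval −1 to 31, power 0.42.

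**7. The opposite direction.** Suppose each arm has one unlisted background event per patient and there is no true excess. If EEN-side contacts raise capture in ECS to 0.6–0.8 against 0.5 in CS (assumed), a false ECS excess appears: 0.6 − 0.5 = 0.1, up to 0.8 − 0.5 = 0.3 events per patient.

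**The case against.** A reader might infer that endpoint 10 is tilted toward ECS, that most harms of EEN rest on spontaneous reports, and that ECSC would look safer than CS by construction. The documents do not support any of these.

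- **Direction.** A form completed before treatment cannot tilt an on-treatment count. If it is used later, under-capture only attenuates (steps 4 and 5). Other features could raise the EEN-side count: the trial is open label, the week-3 review is described under the EEN intervention, and the food reaction log is given to patients coming off EEN. Counting weight gain as a harm could also work against ECS.
- **Most harms.** The documents give no harm profile for EEN. Bloating, nausea or vomiting and diarrhea are already asked, and increased appetite partly covers hunger.
- **Spontaneous reports.** The adverse event section is silent on elicitation, and the adverse event pages of the case report form are not among the documents.
- **ECSC.** Fewer steroid harms with less steroid would be a real effect. Hypothesis 2 compares ECSC with ECS. Both receive EEN, so the missing items do not separate those arms in this way, and a steroid list is apt there.

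It can also be said that this is the tenth secondary endpoint of a pilot, and that EEN tolerability is partly tracked elsewhere through recorded volumes, returned cans, a diary and compliance rules. Those are adherence records, not adverse event ascertainment, and they give no ECS–CS comparison.

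All four points above stand as limits on the claim. None of them supplies endpoint 10 with a harm list that is balanced between the arms and asked on treatment.

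**Conclusion.** The point holds as a gap in ascertainment, not as a demonstrated bias in favour of ECS. Under either reading of the visit label, endpoint 10 lacks what it needs. At visit 2 only, there is no structured on-treatment list. Used on treatment, the list prompts steroid-type events and leaves some foreseeable EEN events unprompted.

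The second reading would shrink a true ECS excess, for example to 9–18 points where prompting would show 27. Those figures rest wholly on the assumed 30% harm rate and capture rates, and they describe one EEN-specific category, not the total event count. The net direction remains uncertain. The change is worth making because it is cheap and improves the safety comparison.

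**What to change.** Rename Appendix 2 as a general adverse events assessment. Add a short EEN block covering formula intolerance or refusal, constipation, hunger and tube problems. Ask every item of all three arms at visit 2, labelled as baseline, and at visits 3 and 4.

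In the statistical section, base endpoint 10 on treatment-emergent events, and tabulate steroid-type and EEN-type items separately by arm. State how weight gain and food-log entries are counted.

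The cost is a slightly longer form, with no added visit or test. The EEN arms may show a less favourable event count than they would without the added questions.
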